6.4 Treatments

6.4.1 Treatments administered

Patients will receive treatment for 12 weeks, either anakinra or placebo depending on the randomization schedule, see Table 3. The anakinra doses that will be evaluated are 2 mg/kg/day (max 100 mg/day) and 4 mg/kg/day (max 200 mg/day). The dose will be adjusted according to actual body weight (rounded to the nearest kg) and will remain the same throughout the study. See dosing instructions in Appendix 3.

The placebo will be given in a corresponding volume of the anakinra dose. These means that:

- Patients randomized to 2 mg/kg/day (max 100 mg/day) and patients with a body weight < 29 kg and randomized to 4 mg/kg/day (max 200 mg/day) or placebo will only require one injection per day.
- Patients randomized to 4 mg/kg/day (max 200 mg/day), or placebo, with a body weight ≥ 29 kg will require two injections per day.

Table 3 Investigational medicinal products

Investigational product	Daily dose	Dosage form	Route	Dosage regimen
anakinra	2 mg/kg (max 100 mg)	Solution for injection in pre-filled syringe	Subcutaneous	Once daily
corresponding volume of placebo	Solution volume equivalent to 2 mg/kg (max 100 mg [0.67 mL])	Solution for injection in pre-filled syringe	Subcutaneous	Once daily
anakinra	4 mg/kg (max 200 mg)	Solution for injection in pre-filled syringe	Subcutaneous	Once daily
corresponding volume of placebo	Solution volume equivalent to 4 mg/kg (max 200 mg [1.33 mL])	Solution for injection in pre-filled syringe	Subcutaneous	Once daily

6.4.2 Identity of investigational medicinal products

The investigational product anakinra is delivered as a sterile solution for injection, pre-filled in a single-use graduated syringe with the strength 100 mg. The total volume of injection is 0.67 mL and the concentration of anakinra in the solution is 150 mg/mL. The pre-filled graduated syringe has a pre-attached 29 Gauge thin wall half inch needle, a butyl rubber plunger and a latex free rigid needle shield.

The placebo is also delivered as a sterile solution for injection, in an identical single-use pre-filled graduated syringe. The placebo consists of the active product vehicle (0.67 mL) but without the active ingredient, anakinra.

The anakinra drug substance is manufactured by [REDACTED] product and placebo are manufactured by [REDACTED]

The IMP is packaged and labeled by [REDACTED] Each kit consists of 7 syringes.

Labeling of IMP complies with national regulatory requirements.

6.4.3 Storage, preparation and administration of IMP

The IMP (anakinra or placebo pre-filled graduated syringes) must be stored at refrigerated conditions at 2-8 °C (36°-46°F) in a secure area at the study center. The investigational product should be kept in its original carton and away from light both at the clinic and when stored by the patient. The IMP should not be frozen or shaken. The IMP will be transported by the patients to their homes in provided cooler bags.

Possible deficiencies related to the handling, quality or identity of the IMP should be reported both to the study monitor and also directly to [contact]. Possible deficiencies related to site distribution or storage of investigational products should be reported in accordance with instructions provided in the pharmacy manual.

6.4.3.1 Preparation and administration of IMP

The IMP is intended to be injected by the patient or the caregiver. Each IMP syringe contains 0.67 mL equivalent to 100 mg anakinra or placebo. Depending on the patient weight and randomized dose, the full content of a syringe or part of the content of a syringe will be injected to match the prescribed dose.

The prefilled graduated syringe(s) should be taken out from cold storage and be placed in room temperature 30 minutes before injection.

The IMP should be administered at the same time each day, preferably in the morning, by a s.c. injection into fat tissue in one of the following areas:

- outer area of the upper arms
- abdomen (except the 2-inch area around the belly button)
- front of the middle thighs
- upper outer areas of the buttocks

The IMP administration will be supervised by the investigator or investigational site staff at the Day 1 visit and the exact time point for the administration will be recorded. At all other occasions when the IMP is self-administered the patient will record the exact time point of the administration in the diary.

The graduated syringes are for single use and must be discarded after use.

See detailed instructions regarding preparation and administration of IMP in the pharmacy manual.

6.4.4 Method of assigning patients to a treatment group

A total of 81 patients will be randomized, 54 patients are planned to be randomized to anakinra treatment and 27 patients are planned to be randomized to placebo. The different treatment groups are;

- placebo (corresponding volume of anakinra 2 mg/kg/day [max 100 mg/day]), or
- placebo (corresponding volume of anakinra 4 mg/kg/day [max 200 mg/day]), or
- anakinra 2 mg/kg/day (max 100 mg/day) or
- anakinra 4 mg/kg/day (max 200 mg/day)

The ratio between the treatment groups is 1:1:2:2, i.e. the ratio placebo:anakinra is 1:2.

The randomization numbers will be generated in blocks. Each block will include the four treatment groups per the ratio described above. The block size will not be revealed before breaking of the blind.

The randomization will be stratified by age at onset of disease (< 16 years, ≥ 16 years) and glucocorticoid use at inclusion (yes, no) with a requirement to randomize at least a third of the patients with an age at onset of disease < 16 years and a third of the patients with an age at onset ≥ 16 years. Medidata Balance Randomization and Trial Supply System will be used for IRS and Biostatistics at DCRI will be responsible for generating the randomization scheme, which will link sequential patient randomization numbers to treatment codes.

6.4.5 Blinding and unblinding

6.4.5.1 Blinded treatment assignment

The treatment assignment will be blinded (placebo and active treatment) for the patients, the investigators and any personnel involved with the study conduct or evaluation at the investigational sites, ARO and sponsor. In order to avoid the need to give all patients two injections daily the placebo will be given in a corresponding volume of the anakinra dose (see 6.4.4).

Unblinding, i.e., breaking the code for an individual patient during the study, is restricted to emergency situations and should only be used under circumstances where knowledge of the treatment is necessary for the proper handling of the patient. The decision to break the code must be made by the investigator. The study monitor and sponsor must as soon as possible be informed about the code break.

Unblinding should be documented according to instructions in the Medidata Balance Randomization and Trial Supply System.

6.4.5.2 Blinded independent joint assessor

To minimize bias from observed efficacy or laboratory changes a blinded independent and trained assessor will perform the joint examination. To improve consistency between evaluations, it is strongly recommended that the assessments are conducted by the same assessor at a site.

6.4.6 Prior and concomitant therapy

Intraarticular, intramuscular and intravenous administration of glucocorticoids are prohibited within 4 weeks prior to randomization and during the study. Other administration of glucocorticoid treatment is allowed as concomitant medication during the study if the patient has had a stable dose for at least 1 week prior to randomization. Maximum dose allowed is 1 mg/kg/day (max 60 mg/day). If the patient is on glucocorticoid treatment, the dose can be tapered starting earliest at the Week 2 visit. The patient must have reached at least ACR50 response with no fever in the preceding 7 days at the visit initiating tapering. A suggested glucocorticoid tapering schedule is provided in Appendix 4. All other glucocorticoid treatment is prohibited during the study except topical and inhaled.

Methotrexate is allowed as concomitant medication during the study if the patient has had a stable dose for at least 8 weeks prior to randomization. The dose should remain stable throughout the study as long as it is well tolerated. If prior treatment with methotrexate, discontinuation is required to be at least 4 weeks prior to randomization.

Initiation of continuous NSAID treatment is prohibited during the study. However on demand treatment is allowed.

Narcotic analgesics are not allowed 24 hours prior any study visit.

Use of the following treatments are not allowed concomitantly with the IMP (wash-out periods before randomization are stated in the exclusion criteria see 6.3.2):

- Intraarticular, intramuscular or intravenous administration of glucocorticoids
- Intravenous immunoglobulins

- Canakinumab or any other IL-1 inhibitor
- Tocilizumab, rituximab or any other immunomodulatory medication
- Etanercept, adalimumab, infliximab, or any other TNF inhibitor (investigational or marketed)
- Dapsone or mycophenolate mofetil, Leflunomide, thalidomide or cyclosporine, 6-Mercaptopurine, azathioprine, cyclophosphamide, chlorambucil, or any other immunosuppressant
- Use of any other investigational drug

Live vaccines is not allowed within 1 month prior to randomization and until after 1 month following the last study dose. Inactivated vaccines may be permitted according to the investigator's discretion. The investigator should instruct the patient to notify the study site about any new medications he/she takes after the start of the study drug. All medications and significant non-drug therapies administered after the patient starts treatment with study drug until Week 16_{TeI} must be listed on the concomitant medication CRF page.

Following the 12 week double blind treatment, the patient will be treated at the discretion of the investigator according to standard of care.

6.4.7 Treatment compliance

IMP accountability records will be kept. The pharmacy and the investigator must maintain accurate records demonstrating date and amount of IMP(s) received, to whom and by whom administered or dispensed (patient-by-patient accounting), and accounts of returned IMP(s) and any IMP accidentally or deliberately destroyed. At the end of the study, any remaining IMP(s) will be returned to identified drug depot for destruction, or destroyed locally. In either case, a certificate of destruction must be issued.

6.4.8 Overdose management

For this study, any dose of IMP greater than dose prescribed will be considered an overdose. No dose-limiting toxicities have been observed during clinical studies and a maximum tolerated dose for anakinra has not been established. No specific treatment is indicated for IMP overdose. If an overdose of IMP is administered, the actual dose taken will be recorded in the CRF, and any untoward medical occurrence associated with an overdose will be recorded the same way as any adverse event (see 6.5.5.1).

6.5 Efficacy, safety, pharmacokinetic, and exploratory assessments

6.5.1 Study schedule

See the schedule of assessments in Appendix 5

6.5.1.1 Screening visit (optional)

The screening may be done at a separate visit before the baseline visit to identify patients that could be suitable for the study and/or to ensure that required lab results are available before randomization (see 6.5.5.6.1). Applicable ICFs must be obtained prior to any screening

activities (see 2.3). Once the ICF has been signed, the patient will be assigned an enrolment number.

Any SAE that occur after the informed consent has been signed must be reported (see 6.5.5.1.4).

6.5.1.2 Baseline visit, Day 1

If a screening visit has not been performed applicable ICFs must be obtained prior to any study related activities. Once the ICF has been signed, the patient will be assigned an enrolment number.

Any SAE that occur after the informed consent has been signed must be reported.

All inclusion and exclusion criteria should be reviewed (see 6.3) to assess patient's eligibility. The laboratory tests that are needed for evaluation of inclusion and exclusion criteria should be performed before randomization (see 6.5.5.6.1). If it is expected that any of the lab results are not available within reasonable time a screening visit should be performed the day before (the eligibility laboratory results are valid for 36 hours). See 6.5.1.1. However, a patient can be randomized before results from a interferon-gamma release assay or a PPD test has been confirmed. If the results from this test is positive, that is not due to vaccination (PPD), the patient must be withdrawn from the study (see 6.3.3).

Data will be collected on medical history (see 6.5.2), demographics (see 6.5.3) and prior and concomitant medication (see 6.4.6). Vital signs (see 6.5.5.2) and physical examination (see 6.5.5.3) will be performed.

If the patient has been found eligible, the patient will be randomized .

As part of ACR the physician global assessment of disease activity, patient or parent global assessment of overall well-being, the patient or parent assessment of physical function, assessment of number of joints with active arthritis and number of joints with limited range of motion will be assessed (see 6.5.4.1). Global assessment of the patient disease related pain (see 6.5.4.2), and a 12-lead ECG (see 6.5.5.4) will be assessed.

Prior to the first IMP administration, blood samples will be collected for central laboratory assessments (see 6.5.5.6.2) immunogenicity assessments (see 6.5.5.5), IL-1Ra/anakinra serum concentration assessments (see 6.5.6) and exploratory inflammatory biomarkers (see 6.5.7). For patients consenting to pharmacogenetic assessment an additional blood sample will be collected at a suitable visit after randomization (see 6.5.7.2).

Finally, the first dose of IMP is to be administered and the time point of administration will be recorded. The patient or patient's caregiver will be instructed how to administer the IMP dose on a daily basis and how to complete the diary (see 9.2) and IMP covering the period until next visit will be dispensed.

Adverse events, will be recorded from the time of the first IMP administration (see 6.5.5.1).

6.5.1.3 Day 4^{Tel} telephone follow-up

A telephone contact will be performed at Day 4 for retention reasons, to follow-up on compliance of study procedures and to answer any additional questions from patients or parents/caregivers. Data will be collected on adverse events. If not possible to reach patient or parent/caregiver this should be documented in the CRF.

6.5.1.4 Week 1 visit

The visit should be scheduled as close as possible to 24 hours after last IMP dose.

Assessments conducted at the visits are the ACR variables, physical examination including complete joint exam, vital signs, concomitant medication and global assessment of the patient disease related pain. If any fever or rash attributable to the disease has occurred during the last 24 hours, this will be recorded. Data from the patient diary will support the evaluation.

Blood will be collected for central laboratory assessments, immunogenicity assessments, IL-1Ra/anakinra serum concentration assessments and exploratory inflammatory biomarkers. Adverse events as well as number of days of absenteeism from school or work since the baseline visit (also recorded for guardians where appropriate) will be recorded. The patient diary will be reviewed to confirm that instructions are followed and IMP covering the period until next visit will be dispensed. After all assessments have been performed, the daily IMP administration can occur.

6.5.1.5 Week 2 visit

The visit should be scheduled as close as possible to 24 hours after last IMP dose.

Assessments conducted at the visit are the ACR variables, physical examination including a complete joint count, vital signs, concomitant medication, and global assessment of the patient disease related pain. If any fever or rash attributable to the disease has occurred during the 7 days preceding the Week 2 visit, this will be recorded. Data from the patient diary will support the evaluation.

Blood samples will be collected for central laboratory assessments, immunogenicity assessments, IL-1Ra/anakinra serum concentration assessments and exploratory inflammatory biomarkers. Adverse events as well as number of days of absenteeism from school or work since previous visit (also recorded for guardians where appropriate) will be recorded. The patient diary will be reviewed to confirm that instructions are followed and IMP covering the period until next visit will be dispensed. After all assessments have been performed, the daily IMP administration can occur.

If the patient is on glucocorticoid treatment the possibility to start tapering can be commenced earliest at the Week 2 visit. The patient should have reached at least ACR50 response with no fever in the preceding 7 days at the visit initiating tapering. See Appendix 4 for suggested glucocorticoid tapering instructions.

6.5.1.6 Week 4 and Week 8 visits

The visits will be scheduled as close as possible to 24 hours after last IMP dose.

Assessments conducted at the visits are the ACR variables, physical examination including complete joint exam, global assessment of the patient disease related pain, vital signs, and concomitant medication. If any fever or rash attributable to the disease has occurred during the 7 days preceding the visit, this will be recorded. Data from the patient diary will support the evaluation.

Blood samples will be collected for central laboratory assessments, immunogenicity assessments and IL-1Ra/anakinra serum concentration assessments. Adverse events as well as number of days of absenteeism from school or work since previous visit (also recorded for guardians where appropriate) will be recorded. The patient diary will be reviewed to confirm

that instructions are followed and IMP covering the period until next visit will be dispensed. After all assessments have been performed at the visit the daily IMP administration can occur.

If the patient is on glucocorticoid treatment consider the possibility to taper if the patient has reached at least ACR50 response with no fever in the preceding 7 days. See Appendix 4 for suggested glucocorticoid tapering instructions.

6.5.1.7 Week 12 visit

The visit will be scheduled as close as possible to 24 hours after last IMP dose.

Assessments conducted at the visit are the ACR variables, physical examination including complete joint exam, global assessment of the patient disease related pain, vital signs, and concomitant medication. If any fever or rash attributable to the disease has occurred during the 7 days preceding the Week 12 visit, this will be recorded. Data from the patient diary will support the evaluation.

Blood samples will be collected for central laboratory assessments, immunogenicity assessments, IL-1Ra/anakinra serum concentration assessments and exploratory inflammatory biomarkers. Inactive disease (see 6.5.4.5) will be evaluated. Adverse events as well as number of days of absenteeism from school or work since previous visit (also recorded for guardians where appropriate) will be recorded. The patient's diary will be reviewed. Finally all IMP should be collected from the patient and accounted for.

For patients enrolled in the repeated-dose PK sampling, this visit should be scheduled on the same day as the last dose of IMP administration is planned. For details regarding the blood sampling procedure and IMP administration see 6.5.6.1.

6.5.1.8 Week 16_{Tel} telephone follow-up

A follow-up telephone call will be made at Week 16_{Tel} (End of study). Data will be collected on concomitant medications and adverse events.

6.5.1.9 Study Drug Discontinuation visit

The visit is performed if the investigator judges that a patient must discontinue study drug before the Week 12 visit. A Study Drug Discontinuation visit should be performed before standard of care treatment is initiated, when possible. If the study drug is discontinued on a scheduled visit, the assessments for the Study Drug Discontinuation visit should be performed instead of the assessments of the scheduled visit, unless the study drug is discontinued at the Week 12 visit.

Assessments conducted at the visit are the ACR variables, physical examination including complete joint exam, global assessment of the patient disease related pain, vital signs, and concomitant medication. If any fever or rash attributable to the disease has occurred during the 7 days preceding the Study Drug Discontinuation visit, this will be recorded. If this visit is performed before the Week 1 visit, fever and rash attributable to the disease during the 24-hours preceding the Study Drug Discontinuation visit will be recorded. Data from the patient diary will support the evaluation.

Blood samples will be collected for central laboratory assessments, immunogenicity assessments, IL-1Ra/anakinra serum concentration assessments and exploratory

inflammatory biomarkers. Inactive disease (see 6.5.4.5) will be evaluated. Adverse events, number of days of absenteeism from school or work since previous visit (for guardians where appropriate) as well as morning stiffness will be recorded. The reason for study drug discontinuation is recorded in the CRF. "Escape criteria" can be evaluated in the CRF. Finally, all IMP should be returned and accounted for.

Patients that discontinue study drug before the Week 2 visit should still return for a Week 2 visit according to original schedule of assessments. If the Study Drug Discontinuation visit is performed within 3 days prior to the Week 2 visit, the scheduled Week 2 visit should be omitted.

A final follow-up call will be conducted 4 weeks after the last IMP administration according to the assessments described for the Week 16_{Tel}.

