5.3 Key secondary objective and endpoints

Objective To demonstrate early onset of efficacy of anakinra versus placebo in Still's disease.

- Endpoints**
- Absence of fever during the 24 hours preceding Week 1.
 - Change from baseline in physician global assessment of disease activity (VAS) at Week 1.
 - Change from baseline in patient/parent global assessment of overall well-being (VAS) at Week 1.
 - Change from baseline in CRP at Week 1.

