### 8.2 Handling of missing data and outliers

#### 8.2.1 Imputation for efficacy endpoints

For all endpoints related to the primary objective the following imputation will be used:

- Patients that discontinue study drug prior to Week 2 will be set to non-responders.
- For patients with missing information in any of the ACR30 components, that specific component will be set to no change. For patients with missing information on fever, the patients will be treated as having a presence of fever.

For the key secondary endpoints the following imputation will be used:

- Patients who have missing information on fever during 24 hours preceding Week 1 will be treated as having a presence of fever in the analysis.
- For the other secondary endpoints no imputation will be performed, i.e., all presentations will be based on observed data.

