#### 8.5.2 Absence of fever

Separate eCRF forms will specifically query whether fever was absent or present in the 24 hours preceding Week 1 or absent/present in the 7 days preceding Week 2.

Absence of fever at subsequent weeks (Week 4, 8 and 12) will be derived based on information recorded in the fever diary during the 7 days preceding each visit. The number of patients with

no missing data on fever will constitute the denominator for the percentage of patients with absence of fever during each week.

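### A stop at the Week 1 visit triggers a 7-day fever and rash question where the Week 1 endpoints need 24 hours, and the SAP does not say how the 24-hour status is then obtained

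*Protocol*

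**What the plan says.** The key secondary fever endpoint is "Absence of fever during the 24 hours preceding Week 1" (Protocol 5.3, repeated in SAP 3.3.3). The Week 1 rash endpoint (Protocol 5.4.1) and the fever part of the Week 1 ACR responses (Protocol 5.2) use the same 24 hours. The ordinary Week 1 visit asks for that window: "If any fever or rash attributable to the disease has occurred during the last 24 hours, this will be recorded" (Protocol 6.5.1.4).

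A stop on a scheduled visit, other than Week 12, changes what is asked. Protocol 6.5.1.9 says that "the assessments for the Study Drug Discontinuation visit should be performed instead of the assessments of the scheduled visit". The same section sets the look-back at that visit to a week ("If any fever or rash attributable to the disease has occurred during the 7 days preceding the Study Drug Discontinuation visit") and shortens it under one condition only: "If this visit is performed before the Week 1 visit, fever and rash attributable to the disease during the 24-hours preceding" the SDD visit are recorded.

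For the analysis, SAP 8.5.2 names the source of the Week 1 value: "Separate eCRF forms will specifically query whether fever was absent or present in the 24 hours preceding Week 1". It derives fever from the diary only for Weeks 4, 8 and 12. SAP 8.2.1 adds that "Patients who have missing information on fever during 24 hours preceding Week 1 will be treated as having a presence of fever". SAP 8.1 assigns assessments made on Days 2 to 11 to Week 1.

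**The concern.** A patient who stops on Day 6 is asked the question that the endpoint needs. A patient who stops at the Week 1 visit is not. The protocol recognises that 24 hours is the right window this early in the trial, but its condition leaves out the case in which the SDD visit takes the place of Week 1.

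The choice of window matters because the two can give opposite answers for a plausible responder. Entry requires a fever episode in the week before randomisation (Protocol 6.3.1), and Protocol 6.2 cites published data in which about 90% of patients were afebrile after three days of anakinra. Fever in the first days that then resolves is therefore an expected pattern. Over 7 days it reads as fever; over the last 24 hours it reads as no fever.

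Three results depend on the 24-hour status of these patients:
- the key secondary absence-of-fever endpoint;
- absence of rash at Week 1;
- the sensitivity analysis of Week 1 ACR30 with absence of fever (Protocol 8.4.2, SAP 12.1.1). It uses the actual data, nearest to Week 1, of patients who stopped for reasons other than progressive disease. For a stop at Week 1, that assessment is the SDD visit.

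**Working it through.** **1. Days covered.** Week 1 is Day 8 with a window of +2 days (Protocol Appendix 5). An SDD visit that replaces it falls on Days 8 to 10, inside the SAP's Day 2 to 11 window for Week 1. The 7 days before Day 8 are Days 1 to 7; the 7 days before Day 10 are Days 3 to 9.

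**2. Fever status by pattern and by derivation**, for a patient who stops at the Week 1 visit:

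| Fever in the 7 days | Status the endpoint asks for | 7-day answer carried to Week 1 (SAP 8.1) | 24-hour item treated as missing (SAP 8.2.1) | Timed diary |
|---|---|---|---|---|
| None | absent | absent | not missing: a 7-day 'no' includes the last 24 hours | absent |
| In the last 24 hours | present | present | present | present |
| Earlier, none in the last 24 hours | absent | **present** | **present** | absent |

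Only the third pattern is mis-scored. The documents do not choose between the last three columns.

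A further reading is possible. Dosing follows the assessments at Week 1 (Protocol 6.5.1.4), so a patient who stops there took the last dose earlier and might be counted as having discontinued before Week 1. Protocol 8.3.5 scores such patients as febrile. SAP 12.3 does not restate that rule.

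**3. Rash.** Carrying over the 7-day answer has the same effect. The missing-data route does not: neither Protocol 8.4.1 nor SAP 8.2.1 imputes rash. The diary holds rash by day (Protocol 6.5.4.4), whereas fever episodes have a time (Protocol 6.5.4.1.7 and 9.2).

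**4. Size.** The plan gives no figure on this point. Inputs are the minimum of 12 patients at 2:1 (SAP 4.2), so 12 × 2/3 = 8 anakinra and 12 × 1/3 = 4 placebo, and the planned 54 and 27 (Protocol 8.1).

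Rescoring one patient moves that arm's rate by:
- 1/8 = 12.5 points (anakinra) or 1/4 = 25 points (placebo) at 8:4;
- 1/54 = 1.9 points or 1/27 = 3.7 points at 54:27.

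Two-sided Fisher tests at 8:4, on illustrative counts without fever, sum the hypergeometric probabilities no larger than that of the observed table:
- 7/8 vs 0/4: C(8,7)·C(4,0)/C(12,7) = 8/792 = 0.010.
- 6/8 vs 0/4: C(8,6)·C(4,0)/C(12,6) = 28/924, plus the equally likely table 2/8 vs 4/4, = 56/924 = 0.061.
- 7/8 vs 1/4: [C(8,7)·C(4,1) + C(8,8)·C(4,0)]/C(12,8) = (32 + 1)/495 = 0.067.

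Rescoring one anakinra patient as febrile takes 7/8 vs 0/4 (0.010) to 6/8 vs 0/4 (0.061). Rescoring one placebo patient takes 7/8 vs 1/4 (0.067) to 7/8 vs 0/4 (0.010). One patient can cross 0.05 in either direction.

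**The case against.** The strongest reply is that the information is collected and only a derivation is unstated. The diary asks about fever daily and records the temperature and time of each episode (Protocol 6.5.4.1.7), it is source data for fever (Protocol 9.3), and 6.5.1.9 says that it supports the SDD evaluation. This stands, and it rules out the stronger reading that a reader might infer: that the endpoint is not measured in these patients and defaults to fever. No section says that a 7-day answer counts as missing, and a 7-day 'no' settles the matter.

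Other limits also stand:
- Mis-scoring needs a stop exactly at Week 1, fever earlier in the week, none in the last 24 hours, and the diary not used. A patient still febrile is scored correctly.
- The main Week 1 ACR analyses may not change. Protocol 8.3.4 counts patients who discontinued as non-responders, and SAP 8.2.1 does so for stops before Week 2 on all endpoints related to the primary objective. SAP 12.2 is narrower: stops before the relevant week.
- One might infer that more placebo patients stop at Week 1, or that the 7-day answer is nearly always 'fever'. The documents give no data on either.
- The SDD eCRF page is not in the documents and may already ask about 24 hours.
- SAP 8.4 tests the key secondary endpoints only after a significant primary result and calls testing of all secondary efficacy endpoints exploratory. At 8:4 and the planning rates of 65% and 25%, the exact power for the primary is about 6.7%.
- The shifts in points are the weight of any single patient; they say nothing about how often this happens.

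What the reply does not answer is that 6.5.1.9, as written, directs the wrong window for these patients, and that SAP 8.5.2 names an eCRF query, not the diary, as the Week 1 source.

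**Conclusion.** The mismatch is real and narrow. For a stop at the Week 1 visit, the protocol's own rule collects fever and rash over 7 days where the endpoints need 24 hours, and the SAP leaves the derivation open. A patient with fever or rash earlier in the week but none in the last 24 hours is recorded as having it if the 7-day answer is carried to Week 1; for fever, the same follows if the 24-hour item is treated as missing.

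The number of such patients is unknown and could be zero. If there is one, at 8:4 the choice of derivation can decide which side of 0.05 the fever comparison falls on; at 54:27 it moves a rate by 1.9 or 3.7 points. This rests on a literal reading of 6.5.1.9, on no 24-hour item on the SDD page, and on 12 patients split exactly 2:1. The documents do not support a claim of general mis-scoring or of bias in a known direction. The gap is worth closing before unblinding because the rule would otherwise be chosen after the affected patients are known.

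**What to change.** In Protocol 6.5.1.9, extend the condition from an SDD visit before Week 1 to one before or in place of the Week 1 visit, so that 24-hour fever and rash status is recorded. When the visit replaces Week 1, record it in addition to the 7-day answer.

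In SAP 8.5.2, state that this 24-hour answer is the Week 1 value when the SDD visit replaces Week 1 and, if it was not collected, that fever status is derived from the timed diary. The sentence should name rash too, since SAP 8.5 has no rash subsection. Asking at the visit is preferable to deriving later, because attribution of fever to the disease is the investigator's judgement (Protocol 6.5.4.1.7).

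The cost is one phrase, one conditional eCRF item and one SAP sentence, with no new visit or procedure. If data collection has ended, the SAP sentence alone can still be added before the SAP is locked ahead of database lock (SAP 5.2).
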